## 1. Comparison Details

### a. Intended aim(s)

To evaluate the comparative risk of dementia onset between patients treated with Anastrozole vs Exemestane or Letrozole for breast cancer.

### b. Primary endpoint

Incident dementia (i.e., Alzheimer's disease, vascular dementia, senile, presenile, or unspecified dementia, or dementia in other diseases classified elsewhere).

## 3. Data Source(s)

Medicare, 2008-2018

#### 4. Study Design Diagrams

[figure not shown]
[figure not shown]

Figure- Alternate analysis approaches

[figure not shown]
- ■ ■ ■ Included person-time
- ■ ■ ■ Excluded person-time

Provides 'on treatment' estimates for the outcome risk and addresses exposure person-time misclassification

### Analysis 1

[figure not shown]

### Analysis 3

[figure not shown]
Addresses misclassification of outcome onset

### Analysis 2

Addresses reverse causation due to preferential treatment initiation related to unrecorded cognitive impairment at study start and informative-censoring

### Analysis 4

Addresses outcome misclassification

## 5. Cohort Identification

### a. Cohort Summary

This study will employ a new user, active comparator, observational cohort study design comparing Anastrozole vs Exemestane/Letrozole. The patients will be required to have continuous enrollment during the baseline period of 365 days before initiation of study drugs (cohort entry/index date). Follow-up for the outcome (dementia) differs between analyses. Follow-up begins the day after drug initiation (analysis 1, 3, 4); 180 days after drug initiation (analysis 2).

### b. Key details regarding cohort creation

#### *Index date:*

- Day of initiation of new Anastrozole vs Exemestane or Letrozole use

#### *Inclusion criteria for analyses 1, 3, 4:*

- Aged  $\geq 65$  years on the index date
- 365 days enrollment in Medicare Parts A, B, and D with no HMO coverage prior to index date
- No use of Anastrozole vs Exemestane or Letrozole, any time prior to index date (all available lookback approach with a minimum of 365 days)
- No diagnosis of dementia any time prior to and including index date
- No history of nursing home admission recorded in any time prior to and including index date
- At least two claims with breast cancer diagnosis recorded in 365 days prior to index date (ICD-9 174.x, 175.x, 233.0, V10.3 or ICD-10 C50.x19, C05.90, Z85.3)

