### b. Covariates:

Demographics	
Age	Region
Gender	Calendar year of index date
Race	Low income subsidy

Dementia risk factors	
Diabetes	Depression
Obesity	Anxiety
Hypertension	Bipolar disorder
Coronary artery disease	Schizophrenia

Markers for healthy behavior, frailty, healthcare use	
Smoking	Number of hospitalizations
Mammography	Number of physician office visits
Colonoscopy	Number of serum creatinine tests ordered
Fecal occult blood test	Composite frailty score
Influenza vaccination	Number of C-reactive protein tests ordered
Pneumococcal vaccination	Osteoporosis
Herpes zoster vaccination	Fractures

Bone mineral density test	Falls
Number of distinct generic agents	Use of supplemental oxygen
Number of emergency room visits	Combined comorbidity score
Number of outpatient visits	Alcohol abuse

Comedication use	
Lithium	Diuretics
Anti-epileptic mood stabilizers	Nitrates
Anti-epileptics (other than mood stabilizers)	Lipid lowering drugs
Atypical antipsychotics	Non-insulin diabetes medications
Benzodiazepines	Insulin
Serotonin-norepinephrine reuptake Inhibitors	Antidepressants
Selective serotonin reuptake inhibitors	Angiotensin II receptor blockers (ARBs)
Tricyclic antidepressants (TCAs)	Angiotensin converting enzyme inhibitors (ACEi)
Typical antipsychotics	Calcium channel blockers
Anticoagulants	Beta blockers
Antiplatelet agents	

Comorbid conditions	
Atrial fibrillation	Chronic liver disease
Coronary artery disease	Asthma
Heart failure	Ischemic heart disease
Stroke or transient ischemic attack	Chronic obstructive pulmonary disease
Peripheral vascular disease	Malignancy
Hyperlipidemia	Drug or alcohol abuse or dependence
Renal dysfunction	Venous thromboembolism
Rheumatoid Arthritis	Hypertension

Other Breast Cancer treatments and Breast Cancer severity indicators	
Chemotherapy	Hormone therapy agents

Anthracyclines (Doxorubicin, Epirubicin) Taxanes (Paclitaxel, docetaxel) 5-fluorouracil Capecitabine Cyclophosphamide Carboplatin Ixabepilone Eribulin Platinum agents (Cisplatin, carboplatin) Vinorelbine Capecitabine Gemcitabine	Tamoxifen Toremifene Fulvestrant Goserelin Leuprolide Estradiol Megestrol acetate Androgens, testosterone

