## 7. Propensity score analysis

We will use a propensity-score (PS)-based approach to account for measured confounding in this study. The PS will be calculated as the predicted probability of initiating the exposure of interest (i.e., the repurposing candidate) versus the reference drug conditional on baseline covariates using multivariable logistic regression constructed separately in each data source. On average, patients with similar PSs have similar distribution of potential confounders used to estimate the PS. Therefore, analyses conditioned on the PS provide effect estimates that are free from measured confounding. For all our analyses, initiators of each exposure of interest will be matched with initiators of the reference exposure based on their PS within each data source. Pair matching will be conducted using a nearest-neighbor algorithm, which seeks to minimize the distance between propensity scores in each pair of treated and reference patients, and a caliper of 0.025 on the natural scale of the PS will be used to ensure similarity between the matched patients.

We report multiple diagnostics for PS analysis in this protocol. First, the PS distributional overlap is provided between two groups before and after matching to ensure comparability of these groups. Next, balance in each individual covariate between two treatment groups is reported using standardized differences.

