## 8. Table for covariate balance

	Crude			PS-Matched		
Variable	Anastrozole (N = 10,926)	Exemestane or Letrozole (N = 6,063)	St. Diff	Anastrozole (N = 5,508)	Exemestane or Letrozole (N = 5,508)	St. Diff
Demographics						
Age, mean (SD)	73.7 (6.1)	73.8 (6.3)	-0.02	73.9 (6.4)	73.9 (6.3)	0.01
Gender, n (%)						
Male	41 (0.4)	40 (0.7)	-0.04	29 (0.5)	28 (0.5)	0.00
Female	10885 (99.6)	6023 (99.3)	0.04	5479 (99.5)	5480 (99.5)	0.00
Race, n (%)						
White	9669 (88.5)	5351 (88.3)	0.01	4820 (87.5)	4855 (88.1)	-0.02
Black	744 (6.8)	407 (6.7)	0.00	400 (7.3)	379 (6.9)	0.02
Hispanic	96 (0.9)	56 (0.9)	-0.01	60 (1.1)	51 (0.9)	0.02
Other	417 (3.8)	249 (4.1)	-0.02	228 (4.1)	223 (4)	0.01
Region, n (%)						
Northeast; n (%)	2188 (20)	1168 (19.3)	0.02	1086 (19.7)	1080 (19.6)	0.00
South; n (%)	3912 (35.8)	2431 (40.1)	-0.09	2174 (39.5)	2156 (39.1)	0.01
Midwest; n (%)	2877 (26.3)	1266 (20.9)	0.13	1207 (21.9)	1210 (22)	0.00
West; n (%)	1936 (17.7)	1189 (19.6)	-0.05	1035 (18.8)	1053 (19.1)	-0.01
Other; n (%)	13 (0.1)	9 (0.1)	-0.01	6 (0.1)	9 (0.2)	-0.02
Calendar year of index date, n (%)						
2014	2409 (22)	1313 (21.7)	0.01	1160 (21.1)	1222 (22.2)	-0.03
2015	2470 (22.6)	1326 (21.9)	0.02	1217 (22.1)	1211 (22)	0.00
2016	2154 (19.7)	1210 (20)	-0.01	1135 (20.6)	1102 (20)	0.02

DREAM study protocol - Comparison 11 Anastrozole vs Exemestane or Letrozole

2017	1950 (17.8)	1110 (18.3)	-0.01	1001 (18.2)	992 (18)	0.00
2018	1943 (17.8)	1104 (18.2)	-0.01	995 (18.1)	981 (17.8)	0.01
Low income subsidy, n (%)	1197 (11)	645 (10.6)	0.01	632 (11.5)	582 (10.6)	0.03
Dementia risk factors, n (%)						
Anxiety	2220 (20.3)	1238 (20.4)	0.00	1142 (20.7)	1125 (20.4)	0.01
Bipolar disorder	109 (1)	71 (1.2)	-0.02	63 (1.1)	61 (1.1)	0.00
Coronary artery disease	1985 (18.2)	1111 (18.3)	0.00	1011 (18.4)	1008 (18.3)	0.00
Depression	1887 (17.3)	1083 (17.9)	-0.02	991 (18)	978 (17.8)	0.01
Diabetes	3114 (28.5)	1788 (29.5)	-0.02	1599 (29)	1621 (29.4)	-0.01
Hypertension	8496 (77.8)	4606 (76)	0.04	4236 (76.9)	4228 (76.8)	0.00
Obesity	2518 (23)	1306 (21.5)	0.04	1249 (22.7)	1223 (22.2)	0.01
Schizophrenia	19 (0.2)	9 (0.1)	0.01	12 (0.2)	9 (0.2)	0.01
Markers for healthy behavior, frailty, healthcare use						
Bone mineral density test, n (%)	4106 (37.6)	1926 (31.8)	0.12	1876 (34.1)	1855 (33.7)	0.01
Colonoscopy, n (%)	1030 (9.4)	601 (9.9)	-0.02	551 (10)	543 (9.9)	0.01
Fecal occult blood test, n (%)	1033 (9.5)	563 (9.3)	0.01	538 (9.8)	524 (9.5)	0.01

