Non-insulin diabetes medications	1847 (16.9)	1068 (17.6)	-0.02	957 (17.4)	965 (17.5)	0.00
SAMA/SABA	1336 (12.2)	744 (12.3)	0.00	680 (12.3)	670 (12.2)	0.01
Anticoagulants	986 (9)	549 (9.1)	0.00	494 (9)	511 (9.3)	-0.01
Anti-epileptic mood stabilizers	117 (1.1)	62 (1)	0.01	57 (1)	56 (1)	0.00
Antiplatelet agents	528 (4.8)	274 (4.5)	0.02	256 (4.6)	263 (4.8)	-0.01
Atypical antipsychotics	157 (1.4)	103 (1.7)	-0.02	91 (1.7)	92 (1.7)	0.00
Benzodiazepines	2888 (26.4)	1674 (27.6)	-0.03	1499 (27.2)	1520 (27.6)	-0.01
Lithium	13 (0.1)	12 (0.2)	-0.02	9 (0.2)	10 (0.2)	0.00
Anti-epileptics (other than mood stabilizers)	1431 (13.1)	807 (13.3)	-0.01	701 (12.7)	728 (13.2)	-0.02
Serotonin-norepinephrine reuptake inhibitors	655 (6)	399 (6.6)	-0.02	345 (6.3)	346 (6.3)	0.00
Selective serotonin reuptake inhibitors	1828 (16.7)	1083 (17.9)	-0.03	953 (17.3)	973 (17.7)	-0.01
Tricyclic antidepressants (TCAs)	345 (3.2)	172 (2.8)	0.02	141 (2.6)	157 (2.9)	-0.02
Typical antipsychotics	23 (0.2)	20 (0.3)	-0.02	15 (0.3)	18 (0.3)	-0.01
Breast Cancer Variables , n (%)						
Breast surgery	9099 (83.3)	3988 (65.8)	0.41	3980 (72.3)	3977 (72.2)	0.00
Chemotherapy	2120 (19.4)	1460 (24.1)	-0.11	1203 (21.8)	1205 (21.9)	0.00

DREAM study protocol - Comparison 11 Anastrozole vs Exemestane or Letrozole

Hormone therapy agents	1088 (10)	865 (14.3)	-0.13	682 (12.4)	682 (12.4)	0.00
Immunotherapy	1 (0)	1 (0)	-0.01	1 (0)	1 (0)	0.00
Radiation therapy	5121 (46.9)	2299 (37.9)	0.18	2228 (40.5)	2236 (40.6)	0.00
Targeted therapy	34 (0.3)	232 (3.8)	-0.25	34 (0.6)	34 (0.6)	0.00
Comorbid conditions, n (%)						
Atrial fibrillation	1081 (9.9)	589 (9.7)	0.01	556 (10.1)	553 (10)	0.00
Asthma	1820 (16.7)	988 (16.3)	0.01	906 (16.4)	891 (16.2)	0.01
Chronic obstructive pulmonary disease	1804 (16.5)	1019 (16.8)	-0.01	932 (16.9)	913 (16.6)	0.01
Chronic liver disease	917 (8.4)	650 (10.7)	-0.08	533 (9.7)	538 (9.8)	0.00
Drug or alcohol abuse or dependence	985 (9)	518 (8.5)	0.02	491 (8.9)	477 (8.7)	0.01
Heart failure	714 (6.5)	414 (6.8)	-0.01	361 (6.6)	375 (6.8)	-0.01
Hyperlipidemia	7634 (69.9)	4107 (67.7)	0.05	3738 (67.9)	3778 (68.6)	-0.02
Ischemic heart disease	1919 (17.6)	1073 (17.7)	0.00	975 (17.7)	974 (17.7)	0.00
Malignancy	10906 (99.8)	6054 (99.9)	-0.01	5500 (99.9)	5499 (99.8)	0.01
Peripheral vascular disease	754 (6.9)	422 (7)	0.00	392 (7.1)	394 (7.2)	0.00
Rheumatoid Arthritis	357 (3.3)	210 (3.5)	-0.01	186 (3.4)	196 (3.6)	-0.01
Renal dysfunction	1319 (12.1)	723 (11.9)	0.01	666 (12.1)	660 (12)	0.00

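### Earlier use of other endocrine drugs is neither excluded nor separated by agent: one pooled row, balanced after matching, cannot show balance on the component drugs

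*Combined protocol and SAP*

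**What the plan says.** Section 5a sets the design: "This study will employ a new user, active comparator, observational cohort study design comparing Anastrozole vs Exemestane/Letrozole". The drug washout in section 5b is "No use of Anastrozole vs Exemestane or Letrozole, any time prior to index date", applied over the whole look-back that the data allow and never less than 365 days; analysis 2 uses the same criterion. No criterion, and no step in the cohort flowchart, removes patients who had other endocrine therapy.

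Section 6b lists, under a single heading for hormone therapy, "Tamoxifen Toremifene Fulvestrant Goserelin Leuprolide Estradiol Megestrol acetate Androgens, testosterone". Section 7 says that "balance in each individual covariate between two treatment groups is reported using standardized differences". In section 8 the whole group appears as one row: "Hormone therapy agents 1088 (10) 865 (14.3) -0.13 682 (12.4) 682 (12.4) 0.00". None of the eight entries has a row of its own.

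Section 9 plans subgroups by age, sex and baseline cardiovascular disease only. None of the four analyses described in section 4 deals with earlier endocrine exposure.

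**The concern.** For a patient who comes to an aromatase inhibitor from tamoxifen or fulvestrant, the index date starts the study drug but not endocrine treatment. Such patients are mixed with patients whose first endocrine drug is an aromatase inhibitor. The two kinds of patient may differ in disease history and in previous hormonal exposure.

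The arms differ on treatment history before matching. The hormone row has a crude standardized difference of -0.13, alongside breast surgery (0.41), targeted therapy (-0.25) and radiation (0.18). It is therefore reasonable to ask whether the kind of prior hormone drug also differs between arms. The pooled row cannot answer this: a composite can be equal in total while its parts differ. If the parts do differ and are related to dementia risk, the matched hazard ratio carries residual confounding that the reported diagnostics would not reveal. All four analyses share the washout, so none of them would bring it to light.

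**Working it through.** **Inputs (section 8).** Crude: 1,088 of 10,926 on anastrozole, 865 of 6,063 on exemestane or letrozole. Matched: 682 of 5,508 in each arm.

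**1. Reproduce the table.** For a binary covariate, d = (p1 - p2) / sqrt{[p1(1 - p1) + p2(1 - p2)] / 2}.
- Crude: p1 = 1,088/10,926 = 0.0996; p2 = 865/6,063 = 0.1427; d = -0.132. The table gives -0.13.
- Matched: 682/5,508 = 0.1238 in both arms; d = 0.00, as in the table.
- Overall: (1,088 + 865)/16,989 = 1,953/16,989 = 11.5% crude; 1,364/11,016 = 12.4% matched.

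**2. What a pooled 0.00 can hide.** The split by agent is not reported, so the splits here are assumptions. Suppose a share a of flagged anastrozole patients and a share b of flagged comparator patients had an anti-oestrogen. The component prevalences are then 0.1238a and 0.1238b, while the pooled row still reads 0.00.
- a = 0.6, b = 0.4: 7.4% vs 5.0%, d = 0.0248/sqrt[(0.0688 + 0.0471)/2] = 0.10.
- a = 0.8, b = 0.2: 9.9% vs 2.5%, d = 0.0743/sqrt[(0.0892 + 0.0242)/2] = 0.31.

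**3. Possible effect on the hazard ratio.** Let RR be an assumed dementia risk ratio for prior anti-oestrogen use; the documents give none. The approximate bias factor is [1 + 0.1238a(RR - 1)] / [1 + 0.1238b(RR - 1)].

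| Split a vs b | RR 0.5 | RR 1.5 | RR 2.0 |
|---|---|---|---|
| 0.6 vs 0.4 | 0.99 | 1.01 | 1.02 |
| 0.8 vs 0.2 | 0.96 | 1.04 | 1.07 |
| 1 vs 0 (extreme) | 0.94 | 1.06 | 1.12 |

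For example, with a = 0.6, b = 0.4 and RR = 1.5, the factor is 1.0371/1.0248 = 1.012. Exchanging a and b inverts each factor, so the direction is unknown.

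**4. Cost of a restricted analysis.** Removing every flagged patient leaves 10,926 - 1,088 = 9,838 and 6,063 - 865 = 5,198 before matching. Within the existing match, 5,508 - 682 = 4,826 per arm remain. If existing pairs must stay whole, between 5,508 - 2 × 682 = 4,144 and 4,826 pairs survive. If events scale with numbers, the standard error of the log hazard ratio rises by sqrt(5,508/4,826) = 1.07 to sqrt(5,508/4,144) = 1.15.

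**The case against.** Several parts of the case on the other side stand.

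- **A reader might infer that the new-user design fails.** It does not. Sections 5 and 6a define new use by initiation of the study drugs, and the washout enforces that over all available look-back. A cohort naive to all endocrine therapy would be a different target population, not the one the plan promised and missed.
- **A reader might take 12.4% as the share of endocrine switchers.** It counts any listed agent, estradiol and androgens included. Among flagged patients the anti-oestrogen share is at most 12.4% and could be well below it. The documents do not state the look-back for covariates. If it is the 365-day baseline, older use is unflagged and the figure understates ever-use.
- **The single propensity-score term is an inference.** The model terms are not spelled out, and the appendix of codes is not in the available text. Rows and listed covariates do not correspond exactly: DMARD and SAMA/SABA have rows but are not listed in section 6b. Chemotherapy, targeted therapy and surgery are also shown as single rows, so the pooling may be only presentational. Even so, balance by agent is not shown.
- **No difference in agent mix between arms is shown.** Two matched patients with different prior agents are not in themselves a defect, because propensity-score matching balances distributions and not pairs.
- **Other severity markers are balanced after matching.** Surgery, chemotherapy, radiation and targeted therapy are at 0.00 and the comorbidity score at 0.01. This reduces the concern about different points of care but does not measure prior endocrine exposure.

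The plan states no biological mechanism. The point needs none: it rests on unlike drugs sharing one indicator.

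**Conclusion.** The point holds as a limited one. The cohort is new-user for the three aromatase inhibitors but mixes patients with and without earlier endocrine therapy. The only reported control for that history is a pooled row whose 0.00 says nothing about its components. Residual confounding is possible and not demonstrated; the documents do not support saying that it is present.

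Its likely size is modest: about 1% to 7% on the hazard ratio for mixes between 60/40 and 80/20 with a risk ratio of 1.5 or 2.0, and 6% to 12% at the 100/0 extreme. All of these inputs are assumptions. The range covers flagged patients only and does not extend to unflagged earlier use. A shift of this size could matter if the true difference between drugs of one class is small. The improvement is worthwhile because it is cheap and concerns a factor that was imbalanced before matching.

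**What to change.** 1. In the propensity score and the balance table, replace the pooled indicator ("Hormone therapy agents") with separate ones, at least: tamoxifen/toremifene; fulvestrant/megestrol; goserelin/leuprolide; estradiol; androgens. Merge very rare groups if the model needs it. Use all available look-back and state it. The data begin in 2008 and index years run from 2014 to 2018, so more than 365 days should be available for many patients.
2. Add one sensitivity analysis, with the propensity score re-estimated and patients re-matched, in those with no prior tamoxifen, toremifene, fulvestrant, megestrol, goserelin or leuprolide. Keep the full cohort as primary.

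**Cost.** No new data are needed: the drugs are already listed, and section 6b says the covariate codes exist. The work is a re-run of the propensity score and one extra analysis. On the flagged counts, that analysis loses up to 11.5% of the crude cohort and up to 865/6,063 = 14.3% of the smaller comparator arm. Its log hazard ratio standard error would be about 7% larger, or up to about 15% if existing pairs are kept instead of re-matched. A longer look-back could flag more patients and raise these losses.

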#### *Inclusion criteria for analysis 2:*

- Aged  $\geq 65$  years on the index date
- 365 days enrollment in Medicare Parts A, B, and D with no HMO coverage prior to index date
- No use of Anastrozole vs Exemestane or Letrozole, any time prior to index date (all available lookback approach with a minimum of 365 days)
- No diagnosis of dementia any time prior to and including index date
- No history of nursing home admission recorded in any time prior to and including index date
- At least two claims with breast cancer diagnosis recorded in 365 days prior to index date (ICD-9 174.x, 175.x, 233.0, V10.3 or ICD-10 C50.x19, C05.90, Z85.3)

- 180-day continuous use of Anastrozole vs Exemestane or Letrozole starting on the index date

c. Flowchart of the study cohort assembly

	Less Excluded Patients	Remaining Patients
All patients		23,466,175
Did not meet cohort entry criteria	-23,372,404	93,771
Excluded due to insufficient enrollment	-59,468	34,303
Excluded based on Dementia Exclusion	-4,796	29,507
Excluded based on Nursing Home Admission	-5,115	24,392
Excluded based on Breast Cancer Diagnosis	-5,939	18,453
Excluded anyone aged <65 at index	-1,464	16,989
Patients in Anastrozole group		10,926
Patients in Exemestane or Letrozole group		6,063
Final cohort		16,989

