Targeted therapy Antibody drug conjugates (Ado-trastuzumab emtansine, Fam-trastuzumab deruxtecan, Sacituzumab govitecan, Sacituzumab govitecan) Monoclonal antibodies (Trastuzumab, Pertuzumab, hyaluronidase, Margetuximab) Kinase inhibitors (Lapatinib, Neratinib, Tucatinib) CDK4/6 inhibitors (Palbociclib, ribociclib, abemaciclib) mTOR inhibitor (Everolimus) PI3K inhibitor (Alpelisib) PARP inhibitors (Olaparib, talazoparib)	Immunotherapy PD-1 inhibitor (Pembrolizumab)
Radiation therapy, beam therapy or brachytherapy	Breast surgery Lumpectomy Mastectomy

ICD-9, ICD-10, HCPCS, and NDC codes used to define the covariates listed above are available in Appendix A.

c. Outcome variables and study follow-up:

- **Primary outcome:** incident dementia, i.e., Alzheimer's disease, vascular dementia, senile, presenile, or unspecified dementia, or dementia in other diseases classified elsewhere. Outcome will be defined by 1 inpatient claim or 2 outpatient claims in analysis 1, 2, 3. In analysis 4, the outcome will be defined by 1 inpatient or 1 outpatient claims and 1 prescription claim for a symptomatic treatment [donepezil, galantamine, rivastigmine, and memantine] within 6 months of each other with outcome date assigned to second event in the sequence.
- Secondary outcomes: Individual component:  
Alzheimer's disease

Condition	ICD-9 and ICD-10 codes
Alzheimer's disease	331.0*, F00*, G30*
Vascular dementia	290.4*, F01*
Senile, presenile, or unspecified dementia	290.0*, 290.1*, 290.3*, 797*, F03*
Dementia in other diseases classified elsewhere	331.1*, 331.2*, 331.7*, 294.1*, F02*

For analysis 1,3, and 4 the follow-up will start the day after initiation of Anastrozole and Exemestane or Letrozole and will continue until the earliest date of the following events:

- The first occurrence of the outcome of interest
- The date of end of continuous registration in the database,
- End of the study period,
- Measured death event occurs,
- The date of drug discontinuation, defined as the date of the last continuous treatment episode of the index drug (Anastrozole and Exemestane or Letrozole) plus a defined grace period (i.e., 90 days after the end of the last prescription's days' supply in main analyses).

For analysis 2, the follow-up will start 180 days after initiation of Anastrozole and Exemestane or Letrozole and will continue until the earliest date of the following events:

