- The first occurrence of the outcome of interest, unless otherwise specified for selected outcomes,
- The date of end of continuous registration in the database,
- End of the study period,
- Measured death event occurs,

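### Analysis 2 starts follow-up at day 180 but excludes dementia only up to the index date, so patients first diagnosed in days 1-180 remain eligible

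*Combined protocol and SAP*

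**What the plan says.** Section 5b sets the index date as "Day of initiation of new Anastrozole vs Exemestane or Letrozole use". For analysis 2, the same section requires "No diagnosis of dementia any time prior to and including index date". This is word for word the criterion for analyses 1, 3 and 4. The one criterion added for analysis 2 is "180-day continuous use of Anastrozole vs Exemestane or Letrozole starting on the index date".

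Section 6c states: "For analysis 2, the follow-up will start 180 days after initiation of Anastrozole and Exemestane or Letrozole". Section 5a gives the same start. Follow-up then ends at the earliest of several events, among them "The first occurrence of the outcome of interest, unless otherwise specified for selected outcomes". On the outcome itself, Section 6c says "Outcome will be defined by 1 inpatient claim or 2 outpatient claims in analysis 1, 2, 3".

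Section 4 gives the purpose of analysis 2: "Addresses reverse causation due to preferential treatment initiation related to unrecorded cognitive impairment at study start and informative-censoring".

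**The concern.** In analyses 1, 3 and 4, follow-up starts the day after initiation, so an exclusion that ends at initiation meets the start of follow-up. In analysis 2 the start moves 180 days later and the exclusion does not move with it. The added criterion concerns drug use. It is not an outcome-free condition.

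The gap matters because of what analysis 2 is for. Impairment that was present but uncoded at initiation can be expected to surface as a diagnosis in the following months, which is the window left open. If such patients stay in and are scored at a dementia code recorded after day 180, already-diagnosed cases enter as early incident events, and the planned 1-year interval hazard ratio (Section 9) is the most exposed. If uncoded impairment also influenced the choice of drug, which is the plan's own worry, these cases would be unevenly split between the arms.

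**Working it through.** **Timeline from the text**

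- Day 0: initiation, which is the index date (Section 5b). The dementia exclusion ends here.
- Days 1-180: continuous use required (Section 5b). No condition on dementia.
- Day 180: follow-up starts (Sections 5a and 6c).

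Take a patient who first meets the outcome on day 60 and keeps filling the drug. She passes every analysis 2 criterion and can be matched. The outcome rule then has two readings:

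- First occurrence since index: her end date (day 60) precedes her start date (day 180), and the plan does not say what happens to her.
- First occurrence within follow-up: she becomes an event at her first qualifying claims after day 180.

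A patient with one outpatient claim before day 180 and a second after it raises a similar question, and no rule covers it.

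**The plan's own counts**

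The Section 5c flowchart reproduces exactly: 23,466,175 − 23,372,404 = 93,771; − 59,468 = 34,303; − 4,796 = 29,507; − 5,115 = 24,392; − 5,939 = 18,453; − 1,464 = 16,989 = 10,926 + 6,063. It has one dementia step and no step for 180-day use, so it probably describes the cohort for analyses 1, 3 and 4. It does not show how analysis 2 treats days 1-180.

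**Share of diagnoses falling in the window**

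Under a constant low hazard, the share of all diagnoses since index that fall in days 1-180 is L / (L + F). L is the window length and F is the mean potential follow-up after day 180.

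- L = 180 / 365.25 = 0.493 years.
- Index counts by year, both arms, unmatched (Section 8): 3,722 (2014), 3,796 (2015), 3,364 (2016), 3,060 (2017), 3,047 (2018); total 16,989.
- Cap: 1,095 days (Section 6c), run here from day 180.
- Assumed: index dates uniform within each year, study end 31 December 2018 (Section 3 gives only the year), no death or disenrolment.

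Mean years after day 180, by index year:

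- 2014: 2.998 (all capped)
- 2015: 2.878 (partly capped)
- 2016: 2.5 − 0.493 = 2.007
- 2017: 1.5 − 0.493 = 1.007
- 2018: 0.254, among the 50.7% (about 1,545) who can reach day 180

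F = (3,722 × 2.998 + 3,796 × 2.878 + 3,364 × 2.007 + 3,060 × 1.007 + 1,545 × 0.254) / 15,487 = 2.09 years.

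Share = 0.493 / (0.493 + 2.086) = 19.1%.

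If everyone had the full 1,095 days after day 180: 180 / (180 + 1,095) = 14.1%. If the 1,095 days ran from index instead: 180 / 1,095 = 16.4%, inside the same range.

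**Number of patients, for scale only**

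The documents give no dementia rate. With N = 2 × 5,508 = 11,016 matched patients and an assumed rate r, the number diagnosed in days 1-180 is N × (1 − exp(−r × 0.493)), ignoring death and discontinuation:

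- 0.5 per 100 person-years: about 27
- 1 per 100: about 54
- 2 per 100: about 108
- 3 per 100: about 162

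The matched set in Section 8 is not labelled by analysis, so N for analysis 2 may differ.

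**The case against.** The strongest reply is that the endpoint is incident dementia and follow-up stops at the first occurrence. A day-60 diagnosis is then the first occurrence, and the patient contributes neither time nor an event. That reading is natural, and programmers may well have implemented it. But the plan does not state it, and it does not repair the eligibility rule: the patient is still admitted and matchable, with an end date before time zero.

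A second reply is that the design diagrams are not available in the text reviewed and may show a longer exclusion window. They may. They would then conflict with the written criterion in Section 5b, and the two would need to be reconciled.

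Three stronger inferences are tempting but not supported:

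- **That 14-19% of analysis 2 events are prevalent cases.** The figure is the share of diagnoses falling in the window. To be miscounted, a patient must also complete 180 days of use, remain alive and enrolled, have qualifying claims after day 180, and be scored under the unfavourable reading.
- **That the nursing-home and enrolment criteria are also wrong because they are not extended to day 180.** Nursing-home admission is not the outcome, and loss of continuous registration already ends follow-up, so someone disenrolled before day 180 has no follow-up time.
- **That analysis 2 will be a subset of the 5,508 pairs.** The plan never says so. Section 7 applies matching to all analyses, and Section 5b defines a separate analysis 2 cohort.

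It is also fair to say that analysis 2 is one of four approaches, and that its other aim, informative censoring, is not touched by this gap.

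**Conclusion.** The point holds. The written dementia exclusion for analysis 2 ends 180 days before follow-up starts, and no other readable criterion closes the gap. This is a stated rule in the wrong place, and it works against the reverse-causation aim of that analysis.

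The size is only roughly bounded. The 14-19% rests on a constant hazard, no death or disenrolment, and the assumed study end. It is a rough ceiling on carried-over events provided early diagnoses do not cluster. If they do, the share in the window is higher. Neither the direction nor the size of any effect on the hazard ratio can be derived from the documents. The gap does not arise in analyses 1, 3 and 4.

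**What to change.** - Change the analysis 2 criterion to no dementia diagnosis at any time before and through day 180, and apply it before propensity-score matching in the analysis 2 cohort.
- State that only first-ever outcomes after day 180 count. Make clear that a dementia claim on or before day 180 makes the patient ineligible, so a claim pair straddling day 180 cannot arise.
- Check the analysis 2 design diagram and reconcile it with the text if it shows a different window.

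The cost is a short wording change, a rerun of analysis 2 if it was programmed otherwise, and slightly fewer events in that analysis.
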